We hypothesize that because HIV-infected individuals are more likely to experience mood disturbance [36, 37] and cognitive dysfunction [38, 39], MET (vs. placebo) will attenuate increases in mood disturbance and cognitive dysfunction (verbal and working memory, executive function, and response inhibition) following 24 hours of smoking abstinence among HIV-infected smokers. We will also test whether MET (vs. placebo) reduces smoking behavior (e.g., cigarettes per day, carbon monoxide) during the 3-week drug run-up. Lastly, we will explore whether there is an added benefit to increasing the dose to 1500 mg (vs. 500 mg) without corresponding adverse effects. The proposed study is uniquely positioned to identify a potential new smoking cessation treatment for a population of smokers with high smoking relapse rates.

CHARACTERISTICS OF THE STUDY POPULATION

1. Target Population

Adult, non-treatment seeking smokers (HIV-: n=54; and HIV+: n=30), between the ages of 18-65, reporting consumption of at least 10 cigarettes per day for at least the past 6 months will be the target population for the study. HIV-infected smokers have been diagnosed with HIV/AIDS (identified through the UPENN CFAR Clinical Core, UPHS PennChart reviews and community-based HIV/AIDS organizations and events; see specific criteria below) and HIV-uninfected smokers will have no diagnosis of HIV, either via blood test (see recruitment strategy below) or self-report.

2. Accrual

One hundred and sixty HIV- and ninety HIV+ subjects will be enrolled in order to have 54 HIV- and 30 HIV+ smokers complete all sessions, accounting conservatively for 30% attrition. Participants will first be screened over the phone and then complete an in-person Intake to ensure final eligibility. Enrolled participants will be randomized to one of the three groups: low dose (500 mg), high dose (1500 mg), or placebo.

3. Key Inclusion Criteria

Eligible subjects will be males and females:

1. 18 years of age or older who self-report smoking at least 5 cigarettes (menthol and non-menthol) per day, on average for the past 6 months.
2. **HIV status**
 - a) HIV-infected smokers: diagnosed with HIV infection and exhibiting viral load of less than or equal to 1000 copies/mL and CD4+ counts of greater than or equal to 200 cells/mm³ within 6 months prior to enrollment.
 - b) HIV-uninfected smokers: no diagnosis of HIV, either via blood test or self-report.
3. Must not currently be interested in quitting smoking.

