 1. Complete the consenting process remotely (per procedure outlined in the Informed Consent section) or in-person. Staff will review the consent form and answer all questions. Staff will then administer a comprehension questionnaire and review incorrect answers as needed. If completed remotely, subjects who are unable to provide an electronic signature may be mailed a physical version of the consent that must be signed and returned to us prior to continuing with the Intake tasks.
 2. Complete mental status exams (MINI and C-SSRS and MADRS, YMRS, Bipolar Disorder Additional Screener, if necessary) with trained research staff member.

3. Complete routine medical history (self-report), including concomitant medication review with a member of the research staff.
4. Complete the Shipley Institute of Living Scale
5. Complete baseline measures
6. Provide urine specimens for drug and (if applicable) pregnancy tests. Participants who test positive for either the urine drug screen and/or pregnancy test may be ineligible. Participants believed to have a false-positive result may continue in the study, with investigator approval.
7. Provide a CO breath sample.
8. Complete physiological measures such as blood pressure, height and weight.
9. Complete brief physical examination (led by a medical professional). If the provider is off-site this will be conducted via telehealth.
10. Provide an 8.5ml blood sample drawn for the assessment of liver function (LFTs and GGT enzyme levels) and creatinine levels. They will receive final confirmation of eligibility via phone call based on the blood test results.

If a participant meets the above eligibility criteria at the Intake, they will finalize their study schedule with staff.

Participants will be asked to refrain from using any study prohibited drugs (note: participants are allowed to take prescription medications not in the exclusion list) throughout their participation in the study.

- **Final Eligibility Phone Call.** When liver function tests have been reviewed and authorized by the Study Physician, a study staff member will call the subjects to inform them of their final eligibility.

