Final Eligibility is defined as: Liver function test results and GGT liver enzyme levels that are no more than 20% outside the normal, clinical range and serum creatinine levels less than 1.5 mg/dL [males], less than 1.4 mg/dL [females]]. Albumin/Globulin ratios 20% outside of normal range will be evaluated for clinical significance by the Study Physician and eligibility will be determined on a case-by-case basis.

Eligible subjects will confirm the study schedule and be randomized to a medication group. Ineligible subjects may be referred to other studies at our center.

- **Baseline Session (Day 0).** Participants will complete a 1.5-hour Baseline session before starting study medication. The Baseline session must be scheduled at least 2 days after Intake, but no more than 30 days can elapse between Intake and Baseline. At the Baseline session participants will:
 1. Provide a CO sample.
 2. Provide urine specimens for drug and (if applicable) pregnancy tests. Participants who test positive for the urine drug screen may be withdrawn from the study. Participants believed to have a false-positive result may continue in the study, with investigator approval.
 3. Complete a blood pressure measurement (See Blood Pressure Procedures under Screening/covariate measures).
 4. Have their blood glucose measured via a handheld glucose monitoring test (see Measures: Screening/Covariates). Subjects who have a low blood glucose level (i.e., less than 70 mg/dl) will be provided a beverage containing at least 15 g carbohydrates (e.g., 4 oz of fruit juice).
 5. Provide two 10 ml and 2 8.5 ml blood samples (less than 3 tablespoons) for examining biomarkers of neuroinflammation (HIV+ subjects only).
 6. Complete questionnaires (smoking rate, concomitant medication review, withdrawal, smoking urges, mood, subjective effects, and side effects). *
 7. MADRS, YMRS, Bipolar Disorder Additional Screener, if necessary*
 8. Complete cognitive tasks which may include tasks assessing working memory (n-back), verbal learning memory (HVLT-R), cognitive flexibility (color shape task), response inhibition (stop-signal task), and delay discounting.

9. Be given instructions for study medication. Medication may be mailed to the participant or provided at the session.

* Some tasks may be completed remotely to reduce the length of in-person visits.

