1. A CO sample to verify abstinence. Mandatory abstinence will be biochemically confirmed by a CO reading of less than or equal to 8 ppm. If the CO reading is not less than 9 ppm, but there is a 50% reduction from the CO collected at the Baseline Visit, this will be considered sufficient and the participant may continue as scheduled. If neither condition is met, but participant reports abstinence, investigator approval will be needed for participant to continue with the session. If a participant smokes (self-reported or biochemically confirmed) during the mandatory abstinence period, they may be withdrawn from the study.
2. A urine sample for a urine drug screen and (if applicable) pregnancy test. If urine drug screen is positive, participants may be withdrawn from the study. Participants believed to have a false-positive result may continue in the study, with investigator approval.
3. Blood pressure (See Blood Pressure Procedures under Screening/covariate measures)
4. Have their blood glucose measured via a handheld glucose monitoring test (see Measures: Screening/Covariates). Subjects who have a low blood glucose level (i.e., less than 70 mg/dl) will be provided a beverage containing at least 15 g carbohydrates (e.g., 4 oz of fruit juice).
5. Report their medication adherence/review pill count*
6. Report side effects and concomitant medication review*
7. Complete questionnaires (mood, smoking urges, attention, and withdrawal symptoms) *

8. MADRS, YMRS, Bipolar Disorder Additional Screener, if necessary*
9. Complete a cognitive task battery (described below)

- 24-H Testing Day Part 2 (Programmed Lapse)

1. Participants will be instructed to smoke one of their own cigarettes in the CIRNA Smoking Laboratory.
2. Following the programmed lapse, participants will complete the assessments of the subjective and rewarding effects of the 'programmed lapse' cigarette (Table 1).

* Some tasks may be completed remotely to reduce the length of in-person visits.

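### With no CO threshold at entry, the Day 23 cut-off of 8 ppm cannot detect undisclosed smoking in participants whose usual CO is already that low

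*Combined protocol and SAP*

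**What the plan says.** All references are to the combined protocol and SAP.

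- **Entry.** Key Inclusion Criteria, item 1, admits people "18 years of age or older who self-report smoking at least 5 cigarettes (menthol and non-menthol) per day, on average for the past 6 months". The Target Population paragraph in the same part of the protocol describes smokers "reporting consumption of at least 10 cigarettes per day for at least the past 6 months". Both are by report.
- **CO at entry.** Intake (Day -1), item 7, asks participants to "Provide a CO breath sample". No minimum value is attached. The Key Exclusion Criteria contain no CO value, and the Final Eligibility Phone Call section turns on blood tests only: "Final Eligibility is defined as: Liver function test results and GGT liver enzyme levels that are no more than 20% outside the normal", with creatinine limits and a review of albumin/globulin ratios.
- **Day 23 check.** 24-H Testing Day Part 1, item 1, gives three routes in order. First: "Mandatory abstinence will be biochemically confirmed by a CO reading of less than or equal to 8 ppm". Second, comparison with the participant's own value: "If the CO reading is not less than 9 ppm, but there is a 50% reduction from the CO collected at the Baseline Visit". Third: "If neither condition is met, but participant reports abstinence, investigator approval will be needed for participant to continue with the session". The same item adds that smoking during the abstinence period, whether self-reported or biochemically confirmed, may lead to withdrawal from the study.

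**The concern.** The primary outcomes are mood and cognition after 24 hours without smoking, so the Day 23 data mean what they are said to mean only if abstinence took place. The first route is an absolute cut-off with no reference to the person's own smoking level. The own-baseline comparison comes in only at 9 ppm or more. Someone whose CO while smoking as usual is 8 ppm or less is therefore classed as biochemically confirmed whether or not they smoked.

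Such entrants are plausible under this plan. The operative criterion is 5 cigarettes per day, the Baseline Session may be held at any time of day, and no interval since the last cigarette is specified for it.

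What is left for these participants is disclosure, and the payment schedule does not favour it. Day 23 pays $40 for the visit, $10 for tasks and a $50 completion bonus ($100 in all, apart from travel), whereas someone found ineligible at a session receives travel money only. The pilot's product is a set of effect sizes for planning later research, and undetected smoking would tend to shrink the abstinence effect among them.

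**Working it through.** The plan states no figure for this point, so there is none to reproduce. The check has three parts.

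**1. What the Day 23 rule requires at each starting CO.** Let b be the Baseline CO in whole ppm. The highest Day 23 reading that passes without investigator approval is m = max(8, 0.5 × b). The fall required is max(0, 1 − m/b).

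- b = 4, 6 or 8: m = 8, fall required 0%.
- b = 9: m = 8, 1 − 8/9 = 11%.
- b = 10: m = 8, 1 − 8/10 = 20%.
- b = 12: m = 8, 1 − 8/12 = 33%.
- b = 16: m = 8, 1 − 8/16 = 50%.
- b = 20: m = 10, fall 50%. b = 30: m = 15, fall 50%.

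At 8 ppm or less an unchanged reading passes, so the CO test carries no information about abstinence. From 9 to 15 ppm it carries some, but asks for less than the 50% fall that the second route treats as sufficient.

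**2. How many participants.** The documents give no CO distribution. Taking shares of 5%, 10% and 20% of the 84 completers as assumptions:

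- 84 × 0.05 = 4.2
- 84 × 0.10 = 8.4
- 84 × 0.20 = 16.8

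**3. Effect on the estimate.** Assume a true abstinence effect of 0.50 SD, and that a fraction f of the affected participants (0.5 to 1) show no abstinence effect because they kept smoking or have no withdrawal. The estimate becomes 0.50 × (1 − share × f).

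- Share 5%: 0.4875 to 0.475, a loss of 0.0125 to 0.025 SD.
- Share 10%: 0.475 to 0.45, a loss of 0.025 to 0.05 SD.
- Share 20%: 0.45 to 0.40, a loss of 0.05 to 0.10 SD.

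For scale, the Statistical Analysis section says that 18 per group gives 95% limits less than half an SD from the mean. This reproduces: t(0.975, 17)/√18 = 0.497 SD. The losses above are 0.0125/0.497 = 3% to 0.10/0.497 = 20% of that half-width.

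**The case against.** A reader might infer that anyone still smoking at a low CO passes Day 23. The documents do not support that. Smoking that the participant reports is itself a ground for withdrawal, a timeline follow-back is taken on Day 23, and the Day 22 call reminds participants that staying in the study depends on abstinence. The gap is limited to smoking that is not disclosed. These safeguards narrow it but do not close it, since each depends on self-report and withdrawal is discretionary.

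A reader might also infer that the effect sizes passed to the next trial are too small. That does not follow. Nothing shows that any affected participant exists, and the share, the fraction and the 0.50 SD are all assumptions. Even so the shift is modest against the precision of 18 per group, in a pilot with no formal hypothesis test. True light smokers with mild withdrawal who meet the criterion belong to the eligible population; including them is not bias in itself. If 10 per day governs, low-CO entrants become less likely.

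Two objections to the remedy have force. An entry floor just above 8 ppm still admits people at 9 to 12 ppm, who need a fall of only 11% to 33%, and a single Intake reading can turn away a real smoker tested long after the last cigarette. The plan is also at Version 15 (August 2020), with enrolment from March 2016 and completion projected for January 2021, so a new entry rule reaches only the last entrants. Neither objection touches the Baseline flag proposed below, which needs no new data.

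**Conclusion.** The gap is real and follows from the text alone: no rule uses CO at entry, and for a participant whose usual CO is 8 ppm or less the Day 23 CO check cannot detect undisclosed smoking. This is more than a missing detail, because the stated rule labels such people as confirmed.

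The number affected is unknown. The likely direction is a smaller estimated abstinence effect, by about 0.01 to 0.10 SD from 0.50 SD. That range depends entirely on the assumed 5% to 20% share, on half to all of those participants showing no effect, and on the assumed 0.50 SD. The point deserves a change but does not undermine the pilot. Separately, the two minimum smoking rates, 5 and 10 per day, contradict each other and must be reconciled.

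**What to change.** 1. For new entrants, add one inclusion line requiring the Intake CO to exceed the study's own abstinence cut-off (greater than 8 ppm). The sample is already taken. The cost is that some light smokers fail screening. The planned enrolment of 250 for 84 completers should not be counted as spare capacity, because the stated 30% attrition would leave 250 × 0.7 = 175, and those figures do not agree.
2. For anyone, including those already enrolled, whose pre-medication Baseline (Day 0) CO is 8 ppm or less, record Day 23 abstinence as *not biochemically verifiable*. Keep the all-completer summary, and beside it give the summaries and effect sizes without these participants, with the number flagged in each arm. The cost is one derived flag and one extra set of summaries.
3. Do not base the flag or any exclusion on Day 21 CO. It is measured after randomisation, and the plan itself hypothesises that metformin lowers CO during the run-up, so selecting on it could remove more participants from the active arms and distort the comparison.
4. Reconcile the minimum smoking rate between the Target Population paragraph and inclusion item 1.

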4. Women of childbearing potential (based on medical history) must consent to use a medically accepted method of birth control (e.g., condoms and spermicide, oral contraceptive, Depo-Provera injection, contraceptive patch, tubal ligation) or abstain from sexual intercourse during the time they are in the study and using transdermal nicotine.
5. If current or past diagnosis of bipolar disorder, eligible if:
 - a. No psychotic features
 - b. MADRS: total score less than 8 (past 4 weeks), suicidal item score less than 1 (past 4 weeks)
 - c. Y-MRS: total score less than 8 (past 4 weeks), irritability, speech content, disruptive or aggressive behavior items score less than 3 (past 4 weeks)
 - d. No psychiatric hospitalization or Emergency Room visits for psychiatric issues in the past 6 months
 - e. No aggressive or violent acts or behavior in the past 6 months
6. Able to communicate fluently in English.
7. Capable of giving written informed consent, which includes compliance with the requirements and restrictions listed in the combined consent/HIPAA form.

4. Key Exclusion Criteria

Subjects who self-report and/or present with the following criteria will not be eligible to participate in the study.

Smoking Behavior:

1. Current enrollment in a smoking cessation program, or use of other smoking cessation medications in the last month or plans to do either in the next 2 months.
2. Daily use of chewing tobacco, snuff and/or snus, or electronic cigarettes.

Alcohol/Drugs:

1. Self-report current alcohol consumption that exceeds 25 standard drinks/week over the past 6 months. Subjects will be told to limit or avoid the use of alcohol while in the study to avoid any adverse reactions to the study medication.
2. Current untreated and unstable diagnosis of substance dependence (eligible if past use and if receiving treatment and stable for at least 30 days). Current untreated and unstable diagnosis of substance abuse requires Study Physician approval.
3. A positive urine drug screen for cocaine, amphetamines, methamphetamines, PCP, barbiturates and ecstasy (MDMA) at Intake, or any testing session (see Measures and Table 1 for details). Participants believed to have a false-positive result may continue in the study, with investigator approval.

Medical:

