We estimate it will take a minimum of 4 weeks for a participant to complete the entire study. However, this time period may be longer to accommodate participant schedules or scheduling difficulties between the Intake and baseline visit. Thus, the maximum duration a participant can be in the study is 10 weeks. Additionally, subjects may be contacted after study participation to clarify self-report data collected during their active participation, if necessary for data analysis.

Projected date of completion of the proposed study

We estimate that 54 HIV- and 30 HIV+ smokers will have completed the study by January 2021, and that analyses and reporting will be complete by April 2021.

DRUGS OR DEVICES

Metformin

The study will be performed using metformin, which is currently marketed for the treatment of type 2 diabetes mellitus.

The proposed study follows the typical dosing regimen for metformin for both the low and high dose groups. The dosing regimen for metformin extended release (XR) will be 500 mg q.d for the low dose. For the high dose, the dosing regimen will be: 500 mg q.d (days 1-7); 1000 mg q.d (days 8-14); 1500 mg q.d (days 15-23). This dosing regimen is documented to be safe and well-tolerated in prior clinical studies with no gender or age effects on its pharmacokinetics [51, 52]. Participants will be instructed to take the study medication once daily with their evening meal. Metformin will be purchased and packaged into blister packs by the Investigational Drug Service at the University of Pennsylvania.

An IND exemption has been granted for this study as the results will not be reported to the FDA to support a new drug indication.

Supply, Preparation, Storage, Packaging and Dispensing of Study Medication

Metformin will be purchased and supplied via the University of Pennsylvania Investigational Drug Service (P1377). Matched placebo will be made in-house using sucrose filler in gel capsules. The IDS will store the medication as per the manufacturer guidelines. Specifically, medication will be stored at room temperature (20 – 25 degrees centigrade) and in airtight containers. Metformin and the matching placebo will be packaged in blister packs. IDS will oversee the labeling of all study medication, and will assign each kit, which contains medication for one subject, a unique Pharmacy Randomization Number (PRN).

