This is a randomized, double-blind placebo-controlled, parallel arm pilot study of the effects of a low vs. high dose of metformin on abstinence-induced negative mood and cognitive deficits. Participants will complete Intake tasks to determine final eligibility before being enrolled into the study. Study visits will be completed either in-person at our center, or remotely (via phone or videoconferencing). Once eligibility is confirmed, subjects will attend a clinic visit (day 0) to establish baseline smoking rate, mood, and cognition. Subjects will then be randomized to one of three groups (low dose: 500 mg, high dose: 1500 mg, or placebo) and will complete 4 additional sessions (days 7, 14, 21, 23) to assess side effects, smoking rate, mood, craving, and withdrawal (Figure 1). Cognitive function will also be assessed on days 21 and 23. Subjects will be instructed to refrain from smoking for 24 hours prior to the laboratory session on day 23.

2. Study Visits

- **Telephone Screening.** Recruited subjects will complete an initial eligibility assessment in the HIV/AIDS clinic or over the telephone. This assessment reduces the likelihood that participants attend an Intake Session only to learn that they are ineligible or to allow us to ascertain physician's clearance should the participants have a medical condition that requires approval (e.g., mild hypertension). If a potential participant cannot be reached by phone, staff may send a text for the purposes of scheduling an initial eligibility screening phone call. This will help to reach potential participants who express interest in the study but do not answer phone calls from unrecognized numbers or do not regularly listen to voicemail messages. Texts will be sent from a central study account and not from the personal cellphones of any research staff. Participants who are initially eligible will be screened against our registration database to confirm that they are not currently participating in another research study at our Center and have not previously reported a condition or circumstance that would make them ineligible for the current study. Those participants who remain initially eligible will move forward with eligibility-determining tasks as part of the Intake session, which will be completed remotely and in-person. The Intake session must occur within 60 days of the initial eligibility screening or the participant will have to be re-screened.

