Urine Drug Screen. The urine drug screen will be administered at Intake and each testing session (baseline, day 21, and day 23). The urine drug screen requires about 30ml of urine and indicates whether the subject has recently taken any exclusionary drugs (cocaine, PCP, amphetamines, methamphetamines, ecstasy and barbiturates). Participants with a positive urine drug screen for any substance listed above other than THC, opiates, or methadone will be deemed ineligible. The rationale for excluding these participants is because one of the primary outcomes in this study is cognitive function. Thus, excluding individuals who screen positive for substances that may interfere with their ability to perform the cognitive tasks (e.g., benzodiazepines may slow reaction times) reduces this potential source of variability. In an effort to remain CLIA-compliant, results from urine drug screening will not be shared with participants. Participants will be informed that the testing is for research purposes only and that they will be informed of their eligibility status, but not of the specific testing results. In addition, the current protocol does not utilize PennChart and therefore, results of the screening will not be added to participants' electronic medical records.

Urine Pregnancy Test. At the Intake and each testing session (Baseline, day 21, and day 23), participants will be supplied with a simple, CLIA-waived urine pregnancy screen and informed that pregnant women are not advised to participate in this research study. Participants will then be instructed to administer the pregnancy test independently and will inform study staff if they would like to continue participation after they have administered the pregnancy screen. Participants will be informed that there is no penalty for discontinuing participation at this point in the visit and that they will still receive travel reimbursement for the visit.

Depression and Anxiety. The Hospital Depression and Anxiety Scale (HADS) [59], a 14-item self-report measure, will assess depression and anxiety symptoms. This scale correlates with clinical ratings of depression and anxiety [59] and is used with HIV-infected individuals [60]. Because depressive symptoms are associated with deficits in cognitive function [61] and lower HAART adherence [62], the HADS will be evaluated as a potential moderator of abstinence effects on cognitive function and relapse. The HADS will be administered at each visit.

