Informed consent will be obtained using the combined consent and HIPAA form approved by the PENN IRB. This process will take place before study data are collected and prior to any treatment. The consenting process may occur remotely in-person as part of the Intake session. If completed remotely, subjects will be contacted via Blue Jeans (HIPAA-compliant) for a videoconference or by phone. Reviewing the consent form will be completed using a RedCap survey and PowerPoint to visualize key points. Staff will email or text the survey link to subjects. The PowerPoint will either be sent to participants or shared using screen share via BlueJeans. Whether in person or remote, staff will review the study description, and all study procedures, potential risks, and information about the study medication will be addressed. Subjects will be given the opportunity to read the consent form in full. Following this, subject questions will be answered, and staff will administer comprehension questions to ensure subject understanding. Any incorrect answers will be addressed by the staff member completing consent. If remote, subjects will indicate within the RedCap survey if they wish to participate and will then be prompted to enter their First and Last name and sign the form using their finger or mouse. Subjects who are unable to provide an electronic signature may be mailed a physical version of the consent that must be mailed back to us prior to continuing with the Intake tasks. If needed, staff may also ask subjects to sign a physical version of the form at their first in-person visit for record keeping. Subjects will be able to download their signed version of the form from RedCap, and staff will also download a version to be saved to the electronic regulatory binder on our secure server, or, printed and placed in our physical binder. If in-person, subjects will receive a physical copy of the combined consent and HIPAA form for their records. Subjects will also be given the PI and Study Physician's contact information should they wish to speak to either of them during the course of the study regarding their consent or the study procedures. The consent process will take place in English, there will be no waiting period, no coercion to participate, and all subjects will be considered competent to provide informed consent (i.e., they will be asked if they understand what they are consenting for).

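### Inclusion item 4 adds an inapplicable second condition, transdermal nicotine use, to the contraception period; the phrase should be deleted (lowest severity)

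*Combined protocol and SAP*

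**What the plan says.** Key Inclusion Criteria, item 4, is the only supplied text that sets a contraception rule. A woman of childbearing potential must agree to a medically accepted method of birth control, or "abstain from sexual intercourse during the time they are in the study and using transdermal nicotine".

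Other sections bear on it:

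- **Study drug.** Under Drugs or Devices, the trial uses metformin XR or matched placebo, packed in 23-day kits. No nicotine product is dispensed.
- **Nicotine patch.** Key Exclusion Criteria, Medication, item 3, excludes current users of cessation medication and names the patch. Smoking Behavior, item 1, excludes cessation medication in the last month or planned for the next two months. Participants are also told to avoid prohibited medication throughout.
- **Pregnancy risk.** Potential Study Risks concludes that metformin should be avoided in pregnancy. It does not discuss nicotine in this connection.
- **Start of dosing.** "Participants will complete a 1.5-hour Baseline session before starting study medication".
- **Length of participation.** Study Duration gives a minimum of 4 weeks and says that "the maximum duration a participant can be in the study is 10 weeks".

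**The concern.** The criterion defines its period by two things joined with *and*: being in the study, and using a product that an eligible, compliant participant does not use. The words look like a carry-over from another protocol, although the documents do not say so.

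Item 4 is an operative eligibility and safety rule, so its wording matters more than a slip in background text would. What is at stake is whether contraception is clearly required while a woman may be taking metformin. Staff should not have to disregard half of the stated period to apply the rule as intended.

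**Working it through.** The plan gives no figure to reproduce, and the point is textual. The check sets item 4 beside the sections that decide what its period can mean.

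**Step 1: dosing days.** The high-dose schedule runs over days 1-7, 8-14 and 15-23, which is 7 + 7 + 9 = 23 days. This agrees with the 23-day kit.

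**Step 2: can the second condition be met?** The trial supplies no patch. Current patch use excludes a candidate, and recent or planned use of cessation medication does too. One route remains: a participant who reports a contraindicated medication after final eligibility may be kept in if the Study Physician or Principal Investigator judges that it does no harm. The condition is therefore essentially never met, though not strictly never.

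**Step 3: the possible readings.**

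| Reading of the period | Dosing days covered (of 23) |
|---|---|
| Both conditions required together | Essentially none |
| *In the study* sufficient by itself | 23 |
| Phrase deleted, leaving *in the study* | 23 |

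**Step 4: does the last row depend on when *in the study* begins?** Study Procedures says that "Participants will complete Intake tasks to determine final eligibility before being enrolled into the study", whereas Study Duration counts the wait between Intake and Baseline within participation. For dosing this makes no difference. Medication starts only after the Baseline session, which follows both Intake and confirmed eligibility. All 23 dosing days fall inside the period on either start.

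**Step 5: is the rule stated correctly elsewhere?** Medical exclusion item 1 excludes women who report being pregnant, planning a pregnancy during the study or breastfeeding, and it schedules urine tests. It sets no contraception requirement. Inclusion item 7 refers to restrictions in the consent form, which is not in the supplied text.

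**The case against.** The strongest reply is that nobody would apply item 4 as a joint condition. On that reading it would ask nothing of almost any eligible woman, so *in the study* must be the operative part. The planned-pregnancy exclusion, which is framed by the whole study, points the same way. This largely stands, and it is why the weight is low. It does not make the extra phrase correct.

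Existing safeguards also count:

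- Urine tests are scheduled at Intake, Baseline, Day 21 and Day 23, and a positive test at Intake may make a candidate ineligible.
- The risk section reports that metformin was not teratogenic in rats and rabbits at the doses it states.
- Consent Process says that "all study procedures, potential risks, and information about the study medication will be addressed", so participants may be given the right instruction.

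These points reduce the practical risk. They do not replace a contraception rule: tests detect pregnancy rather than prevent it, none is scheduled in the 21 days between Baseline and Day 21, and "Participants will then be instructed to administer the pregnancy test independently". The planned-pregnancy exclusion does not address unplanned pregnancy.

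A reader might infer something stronger: that the protocol leaves women without any contraception requirement, or that some number of participant-days went unprotected. The documents do not support that. It depends on the less likely reading of *and*, it ignores the possibility that the consent form is correct, and the documents give no number of women of childbearing potential. Nor does an uncertain start to *in the study* enlarge the defect, since the dosing days are covered either way.

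**Conclusion.** Wrong as written, at the lowest severity. Item 4 contains a condition that does not apply to this trial. The intended period is probably the time in the study, but the literal joint reading would cover essentially none of the 23 dosing days of a drug that the protocol says to avoid in pregnancy.

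The conclusion assumes that the stated period governs both options in item 4 (birth control and abstinence) and that no unsupplied document overrides the item. The consent form could show that participants were told the right thing. The protocol text would still need to match it. There is no consequence for visits, sample size or analysis.

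**What to change.** In Key Inclusion Criteria, item 4, strike the last four words of the quoted phrase, from *and* onward, so that the requirement applies for as long as the woman is in the study. Deletion is safer than naming metformin in place of the patch, because a replacement would leave a second condition that could again be read as limiting the first.

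Check the consent form for the same wording and correct it if present. If the sponsor wants an explicit end point, the same amendment can say whether the 7-day post-dose follow-up used for adverse event reporting is included. This is optional and not needed to cure the error.

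The cost is one phrase in the next amendment, plus matching consent wording if it is affected.
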